### DDD (Defined Daily Dose)

According to WHO "The DDD is the assumed average maintenance dose per day for a drug used for its main indication in adult"

In the absence of electronic medication management systems, the Defined Daily Dose (DDD) is a valuable metric for assessing drug consumption. The Anatomical Therapeutic Chemical (ATC)/DDD methodology, endorsed by the World Health Organization (WHO), is an internationally recognised standard for evaluating drug usage. Guidelines for calculating DDD can be found on the WHO website [here](#). In this study, we will apply the WHO ATC/DDD methodology to determine DDD, with the aim of producing high-quality, practical, and comparable drug utilisation statistics (2).

Drug utilisation data expressed in DDDs offers an approximate estimate of consumption but does not precisely reflect actual usage. DDDs serve as a standardised unit of measurement, unaffected by factors such as price, currency, packaging size, or strength, allowing researchers to examine trends in drug utilisation and compare usage across different population groups.

To calculate the Defined Daily Dose (DDD) for each antibiotic, use the following steps:

1. **Identify the Route of Administration:** Confirm the administration route (e.g., IV, oral) for each antibiotic dose, as the DDD value varies with the route.
2. **Total Dose Administered:** Sum the total dose of each antibiotic administered per patient, as recorded in the dataset.

## STATISTICAL ANALYSIS PLAN

3. **Apply DDD Standard Values:** Divide the total dose administered by the standard DDD value for each antibiotic (specific to its route of administration) provided by the WHO ATC/DDD Index.

### Example of a DDD calculation

#### Scenario

A 57-year-old male patient was admitted to the hospital with a severe respiratory infection and was prescribed intravenous amoxicillin as part of his treatment. To manage the infection, the medical team ordered a 1-gram dose of IV amoxicillin administered every 8 hours.

#### Treatment Summary

- **Dosage per administration:** 1 gram of IV amoxicillin
- **Frequency:** Every 8 hours (3 times per day)
- **Total doses administered over the course of treatment:** 13 doses

#### DDD Calculation

To assess antibiotic use, the team calculates the Defined Daily Doses (DDDs) based on the WHO DDD standard for IV amoxicillin, which is 3 grams per day.

1. **Total dose administered:**
  - Total dose = 1 gram × 13 doses = 13 grams
2. **Total DDDs:**
  - Total DDDs = Total dose administered / WHO DDD for IV amoxicillin
  - Total DDDs = 13 grams / 3 grams = approximately 4.33 DDDs

#### DDD Patient Days

Drug utilisation figures should ideally be presented using a relevant denominator for the health context. In the hospital setting, this would be the number of patients or number of bed days in the setting and period monitored. Description and calculation of the most common indicators such as DDD/patients and DDD/100 bed days, DDD/1000 population/day gives an approximate measure of how many people are taking an antibiotic on any given day. Alternatives include:

- DDD per 1000 inhabitants per day
- DDD per 100 bed-days

#### Definition of DDD per 1,000 Patient Days:

- DDD per 1,000 patient days is a standardized measure that compares the total amount of antibiotics used (in DDDs) to the number of patient care days, adjusted to a standard of 1,000 patient days. This helps compare antibiotic consumption across different settings, regardless of patient volume.
- Formula for DDD per 1,000 Patient Days:
  - The formula is:

$$\text{DDD per 1,000 patient days} = \frac{\text{Total DDD}}{\text{Total patient days}} \times 1,000$$

#### Example calculation of DDD per 1,000 Patient Days:

- Suppose we have the same three patients with the following hospital stays:
  - Patient 1: 5 days

## STATISTICAL ANALYSIS PLAN

- Patient 2: 3 days
- Patient 3: 7 days
- Total patient days = 5 + 3 + 7 = 15 patient days.
- Suppose the total DDD (Defined Daily Dose) for all patients combined is 20.

### Applying the Formula:

$$\text{DDD per 1,000 patient days} = \frac{20 \text{ DDDs}}{15 \text{ patient days}} \times 1,000$$

### Breaking Down the Calculation:

First, divide the total DDD by the total patient days: 20/15=1.3333

Then, multiply by 1,000 to standardize: 1.3333×1,000=1,333.33

The DDD per 1,000 patient days is 1,333.33.

### 4.2 Considerations for timepoints in calculating Length of Therapy (LOT), Days of Therapy (DOT), and Defined Daily Dose (DDD)

Length of Therapy (LOT)	Days of Therapy (DOT)	Defined Daily Dose (DDD)
Starting Point: Enrolment date and time.	Starting Point: Enrolment date and time.	Starting Point: Enrolment date and time.
Stopping Point: Actual antibiotic stopping time as recorded by the treating team.	Stopping Point: Antibiotic stopping time as per treating team's decision.	Stopping Point: Antibiotic stopping time as per treating team's decision.
Exceptions:  Recurrent Infections: Censor the LOT during recurrent infection episodes.  Left Against Medical Advice (LAMA): Consider the date the patient left as the stopping point.  Transfer to Another Hospital: Use the transfer date as the stopping point.  Atypical Cases: Determine a reasonable stopping date through team discussion.	Exceptions:  Same as those applied in the LOT calculation, using specific stopping points for recurrent infections, LAMA, transfers, and atypical cases.	Exceptions:  Same as those applied in the LOT and DOT calculation, using specific stopping points for recurrent infections, LAMA, transfers, and atypical cases.

---

**STATISTICAL ANALYSIS PLAN****4.2 Atypical Cases in PROCALBAN:**

1. **Antibiotic Management:** For cases where an alternative diagnosis is confirmed, the stopping date for empirical antibiotic therapy will be recorded as the actual stop date.
2. **Alternative Diagnosis:** If antibiotic therapy is continued despite the confirmation of an alternative diagnosis, such as Melioidosis (which requires a prolonged course of antibiotics), the date on which the treating team identified this alternative diagnosis will be considered as the stopping date for the initial antibiotic treatment.
3. **Additional Diagnoses:** For cases where an additional diagnosis accompanies the initially suspected infection and antibiotic therapy is continued, the full duration of the antibiotic course will be included in the outcome analysis (e.g., Enteric Fever combined with Viral Infection).
4. **Sepsis Mimickers:** In cases where sepsis-like symptoms are attributed to other conditions, such as cancer, connective tissue diseases, or suspected/confirmed tuberculosis, the duration of empiric antibiotic treatment given before an alternative diagnosis is confirmed through clinical assessment, laboratory findings, or radiological evidence will be used for outcome analysis.
5. **Discrepancies in Diagnosis:** If there is a disagreement among investigators regarding the final diagnosis, a third investigator, who has not previously reviewed the case, will assess it to determine the most appropriate antibiotic duration based on the case's clinical details.

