#### 2.1.2 Primary endpoint

**Length of antibiotic treatment:** number of days of antibiotic treatment during the study period (till 28 days after hospital discharge). The primary outcome data for participants with recurrent infections will be censored at the time of recurrent infection diagnosis.

---

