### Randomisation and blinding

Consecutive patients with suspected sepsis admitted at CMCH are eligible for enrolment, provided informed consent is obtained. After eligibility is confirmed, the patient is randomised to either the experimental (procalcitonin) arm or control (standard therapy) arm. Randomisation and treatment allocation is determined by a central computerized binary sequence number generator in a 1:1 ratio with pre-determined block sizes by the study statistician. The study statistician designs the randomisation schedule. The subject's randomisation number is on the sealed opaque envelope as well as on and insert inside the envelope. The trial staff opens the envelopes sequentially for enrolled trial participants and allocates the patient to the treatment arm that is denoted on the insert of that envelope. The allocated arm is noted on the eCRF and other applicable documents. The medical staff and patients are not blinded to intervention randomisation.

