**4.1 Guide to the calculation of the Length of Therapy (LOT), Days of Therapy (DOT) and the Defined Daily Dose (DDD)**
**Length of therapy (LOT) calculation.**

LOT is defined as the number of days of antibiotic treatment during the study period. Length of treatment will be measured from the day of enrolment to completion of the study follow up (28 days after hospital discharge). The primary outcome data for participants with recurrent infections will be censored at the time of recurrent infection diagnosis, i.e. the recurrent date will be used as the stop date in the calculation of LOT. If the recurrent infection occurs after the patient already stopped antibiotics for the initial presenting infection, the actual stop date of the last dose of antibiotics administered for the initial infection will be used in the LOT calculations and not the recurrent infection date.

The stop date for each antibiotic will be when the treating team discontinues it. In special circumstances, such as patients who left the hospital against medical advice or were transferred to another facility, the stop date will be recorded as the date they left or were transferred, as it was not feasible for the study team to track antibiotic data consistently in both arms beyond these points. If a patient developed an alternative diagnosis during the study that required an extended or modified antibiotic regimen, each case was reviewed individually by an investigator panel to determine the maximum antibiotic duration that could be included in the analysis.

**Scenario 1:** As an example, suppose patient A was admitted to the hospital on 02 February 24 at 10:00 AM due to a urinary tract infection. At 4:00 PM the same day, this patient was enrolled into the PROCALBAN study and was discharged from the hospital on 08 February 24 at 10:00 AM. This patient received intravenous ceftriaxone, 1 gram administered every 12 hourly from the date of enrolment and then upon discharge, this patient was prescribed oral cefuroxime, 500mg every 8 hours, for a duration of 7 days i.e. the actual stop date time for this oral cefuroxime will be subsequently recorded in the database by the end of follow-up for this patient. The calculation of LOT (the primary outcome) will proceed as follows:

1. Hospital stay duration during enrolment will be calculated as follows:
  - Enrollment: February 2nd, 4:00 PM
  - Discharge: February 8th, 10:00 AM
  - Hospital stay duration:

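### For atypical or disputed-diagnosis cases the SAP lets investigators set the antibiotic duration counted in the primary endpoint by judgement, in conflict with its own date-based rules

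*SAP*

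**What the plan says.** Section 2.1.2 defines the primary endpoint as a count of antibiotic treatment days up to 28 days after discharge. The timepoints table (Section 4.2) gives the default stopping point for LOT: "Actual antibiotic stopping time as recorded by the treating team".

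Three places in the appendix replace that record with a decision by study staff:

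- **Section 4.1, LOT calculation.** For an alternative diagnosis that needed a longer or changed regimen, "each case was reviewed individually by an investigator panel to determine the maximum antibiotic duration that could be included in the analysis".
- **Section 4.2, timepoints table, exceptions.** For atypical cases: "Determine a reasonable stopping date through team discussion". The DOT and DDD columns adopt the same exceptions.
- **Atypical Cases in PROCALBAN (also numbered 4.2), item 5.** When investigators disagree about the final diagnosis, a third investigator "will assess it to determine the most appropriate antibiotic duration".

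Items 1 to 4 of the Atypical Cases list are tied to dates. They use, respectively, the actual stop of empirical therapy, the date on which the treating team identified the alternative diagnosis, the full course, and the time before an alternative diagnosis was confirmed.

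On independence, the only condition is that item 5 uses "a third investigator, who has not previously reviewed the case". On blinding, Section 2.2 says: "The medical staff and patients are not blinded to intervention randomisation".

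**The concern.** LOT is something that can be observed. A standard such as most appropriate, maximum or reasonable asks what ought to count, and the SAP gives no criterion for applying it. Item 5 is the clearest instance: the dispute is about the diagnosis, but the ruling is about the outcome value.

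Two things are at stake. The first is reproducibility: two statisticians working from this SAP could derive different primary values for the same patient. The second is bias. The trial tests whether shorter courses follow when procalcitonin guides stopping. If those who decide how many days count know the arm or the procalcitonin results, their view of a suitable duration may differ by arm. These cases largely stay in the main analysis, because Section 3.3 keeps patients with an alternative non-infection diagnosis in the ITT set.

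**Working it through.** **1. The rules applied to one patient.** Take a patient with an alternative diagnosis that needs extended antibiotics. Let E be enrolment, D the date on which the treating team identified that diagnosis, and S the recorded stop, with D before S.

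| Rule | Stop date used | LOT |
|---|---|---|
| Atypical Cases, item 2 | D | D − E |
| Section 4.1 panel | up to a maximum M chosen for the case | the smaller of S − E and M |
| Section 4.2 timepoints table | a date R agreed in discussion | R − E |
| Item 5, if the diagnosis is disputed | a duration A chosen by the third investigator | A |

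Only the first row can be computed from recorded dates. Nothing requires M, R or A to agree with item 2, and no order of precedence is given. Item 5 does not need to rule on duration at all: once the diagnosis is settled, it determines which of items 1 to 4 applies, and that item gives the stop date.

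**2. The planned sample size, needed for the standard error.** Inputs from Section 2.3: difference 2 days (5.2 against 3.2), SD 8, alpha 0.05, power 80%. Sidedness is not stated; two-sided reproduces the figure. The normal approximation gives n = 2 × (1.960 + 0.842)² × 8² / 2² = 251.2, so 252 per arm. The t-test version gives 252.13, so 253 per arm and 506 in total, as stated.

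**3. Possible size.** The SAP gives no number of adjudicated cases, so the following inputs are assumptions. Let f be the share of patients adjudicated, taken as equal in both arms. Let d be the arm difference in mean days removed by judgement among them.

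Shift in the mean LOT difference = f × d. Standard error = 8 × √(2/253) = 0.711 day.

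Type I error = Φ(−1.96 + fd/0.711) + Φ(−1.96 − fd/0.711). Power is recomputed at a difference of 2 − fd days, that is, with the shift towards the null.

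| f | d (days) | Shift (days) | Share of 2 days | Type I error | Power if towards null |
|---|---|---|---|---|---|
| 5% | 1 | 0.05 | 2.5% | 0.051 | 0.78 |
| 5% | 5 | 0.25 | 12.5% | 0.064 | 0.69 |
| 10% | 3 | 0.30 | 15% | 0.071 | 0.67 |
| 20% | 1 | 0.20 | 10% | 0.059 | 0.72 |
| 20% | 5 | 1.00 | 50% | 0.290 | 0.29 |

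With no shift, the values are 0.05 and 0.80.

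**The case against.** The best defence is that the three places describe one adjudication process. The timepoints table refers to atypical cases, a section of that name follows, and items 1 to 4 there are date-based. On this reading the third investigator works within those items, and the panel's maximum only caps observed days. That may well be the intention, but the text does not say so. None of the three places refers to items 1 to 4, item 5 names duration, and Section 4.1 speaks of individual review. The conflict stands.

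Four stronger readings are tempting but not supported:

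- **That the primary outcome as a whole becomes opinion.** It does not. The default is the recorded stop time, and judgement enters only for atypical or disputed cases. The PP analysis also drops alternative non-infectious diagnoses, which is a partial check. However, PP follows the main ITT analysis and is not stated to drop every disputed case.
- **That the reviewers knew the arm.** Section 2.2 mentions medical staff and patients, not the panel or the third investigator. The SAP is silent on their masking, and a protocol not at hand may cover it. Nor does the SAP say that the procalcitonin series was in the files. Masking would not in any case resolve the conflict between the rules.
- **That values have already been set this way.** The past tense in Section 4.1 suggests it but does not prove it.
- **That the bias would favour the intervention and could never be detected.** The direction is open: removing more days from the control arm would shrink the effect. Recorded and adjudicated LOT can be compared by arm, since the first worked example in Section 4.1 has actual stop times entered in the database.

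**Conclusion.** The point holds for atypical and disputed cases. The SAP states judgement-based rules for the primary value that conflict with its own date-based rules, in a non-blinded trial and with no masking of these reviewers stated. In those cases LOT, and with it DOT and DDD, is not reproducible and is open to arm-dependent judgement.

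The size cannot be known from the SAP. Under the assumed 5–20% of patients and 1–5 days, the shift is 0.05 to 1.0 day in either direction, from negligible to half of the planned effect. The range shows what the rule permits; it does not estimate bias. The error rates also assume the planned SD of 8 and 253 patients per arm. The correction is worth making because the derivation rule is faulty whatever the count, and correcting it is cheap.

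**What to change.** Change the SAP as follows:

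1. **Item 5:** the third investigator settles the diagnosis only. The stop date used in the analysis then follows mechanically from items 1 to 4 and the recorded dates.
2. **Section 4.1 and the timepoints table:** replace the panel-set maximum and the date agreed in discussion with a reference to items 1 to 4.
3. **Masking:** carry out the diagnosis review on files with arm and procalcitonin results removed, where feasible.
4. **Unchanged:** keep the existing rules for recurrent infection, leaving against medical advice and transfer. Using recorded stop dates for every ITT patient would go too far. It would cancel those rules and the cut at an alternative diagnosis, and Section 4.1 says that antibiotic data could not be tracked consistently after departure or transfer.
5. **Reporting:** give the number of adjudicated cases and the days removed, by arm.
6. **Sensitivity analysis:** repeat the ITT analysis with recorded antibiotic stop dates for the adjudicated cases.

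These changes concern only which days are counted, not how patients are treated. The cost is SAP wording, some file redaction and a little extra analysis of recorded dates. One limit remains: items 2 and 4 still depend on when an alternative diagnosis was identified or confirmed in a non-blinded trial. The sensitivity analysis would show how far the result depends on that, but it cannot separate reviewer judgement from true differences between arms.

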## STATISTICAL ANALYSIS PLAN

[figure not shown]

Figure 2: Pictorial Representation of ITT and PP Analysis Plan for Participants

---

**STATISTICAL ANALYSIS PLAN**

---

